Appendix 2 ***Optional Shorter Infusion Substudy (cont.)***

OBJECTIVES

The primary objective of this study is to evaluate the rate and severity of infusion-related reactions (IRRs) of the ocrelizumab 600-mg infusion administered over the course of 2 hours, instead of the currently approved duration of 3.5 hours, in patients with MS who have had prior treatment with ocrelizumab in MN30035 (CHORDS), as measured by the rate and frequency of National Cancer Institute Common Terminology Criteria for Adverse Events, Version 4.0 (NCI CTCAE v4.0) Grade 3 and 4 IRRs.

STUDY DESIGN

This is an open-label, non-randomized substudy to MN30035 designed to evaluate the safety and tolerability of ocrelizumab infused over a shorter time period than the approved administration rate. Patients who complete their Week 72 ocrelizumab infusion and do not experience any serious IRR (see Section 5.2.2 for seriousness criteria) throughout the main study will be eligible to enroll in this optional substudy and receive one additional shorter infusion of ocrelizumab at the Week 96 visit.

Premedication in the substudy will be administered per the main study methods (Section 4.3.3). Ocrelizumab will then be administered as a single 600-mg dose at a shorter infusion rate (i.e., over the course of approximately 2 hours instead of 3.5 hours) than in the main study.

Ocrelizumab infusion rate will be slowed and/or stopped if a patient experiences a Grade 3 or higher IRR or other serious adverse event.

Patients who received ocrelizumab at a shorter infusion rate at the Week 96 visit will return for a substudy follow-up visit approximately 30 days after treatment.

The end of the treatment period in the substudy is defined as the date when the last patient in the substudy completes the substudy follow-up visit (Week 100).

Planned Total Sample Size

This substudy will enroll approximately 100 patients from MN30035 who did not experience any serious IRR throughout the main study.

OUTCOME MEASURES

Safety Outcome Measures

- *Rate and frequency of Grade 3 or 4 IRRs with onset on or after the shorter ocrelizumab infusion at Week 96 and at the substudy follow-up*
- *Changes in physical findings and vital signs with onset on or after the shorter ocrelizumab infusion at Week 96 and at the substudy follow-up*

Ocrelizumab—Genentech, Inc.
80/ Protocol MN30035, Version 5

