5. ASSESSMENT OF SAFETY

5.1 SAFETY PLAN

Ocrelizumab is currently in clinical development for the treatment of MS. Identified and potential risks associated with ocrelizumab treatment will continue to be closely monitored throughout the clinical program. Patient safety during the ocrelizumab program is ensured by targeting the most appropriate patient population, stringent safety monitoring by the Sponsor, and protocol-specified ocrelizumab treatment interruption criteria. Patients will be evaluated clinically and with standard laboratory tests before and at regular intervals during their participation in this study. Safety evaluations will consist of medical interviews, recording of adverse events, physical examinations, and standard laboratory measurements. Adverse events will be graded according to the National Cancer Institute (NCI) Common Terminology Criteria for Adverse Events (CTCAE) v4.0.

Ocrelizumab—Genentech, Inc.
41/ Protocol MN30035, Version 5

Administration of ocrelizumab will be performed in a hospital or clinic environment under close supervision of the investigator or a medically qualified staff member. All adverse events and serious adverse events will be recorded during the study for at least 24 weeks after the end of the treatment period and throughout safety follow up. Safety assessments will include the incidence, nature, and severity of (serious) adverse events graded per the NCI CTCAE v4.0. Safety assessments will be conducted per the schedule of activities in [Appendix 1](#).

The identified and potential safety issues anticipated in this study are reported in the Ocrelizumab Investigator's Brochure. In addition, measures intended to avoid or minimize these issues, are outlined in the following sections.

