5.1.4 Management of Patients Who Experience Specific Adverse Events

Guidelines for management of specific adverse events are outlined in [Table 2](#). Additional guidelines are provided in the subsections below.

Table 2 Guidelines for Management of Specific Adverse Events

Event	Action to Be Taken
Mild to moderate IRR	
• If the event that a patient experiences is a mild to moderate IRR (e.g. headache), the infusion rate should be reduced to half the rate at the time of the event.• This reduced rate should be maintained for at least 30 minutes. If tolerated, the infusion rate may then be increased according to the patient's initial infusion schedule.
Severe IRR (or complex of flushing, fever, and throat pain)	
• If a patient experiences a severe IRR or a complex of flushing, fever, and throat pain symptoms, the infusion should be interrupted immediately and the patient should receive symptomatic treatment.• The infusion should be restarted only after all symptoms have resolved.• The initial infusion rate at restart should be half of the infusion rate at the time of onset of the reaction.

Event	Action to Be Taken
Life-threatening or disabling IRR (e.g., anaphylaxis)	
 Immediately stop ocrelizumab if there are signs of a life-threatening or disabling IRR during an infusion, such as acute hypersensitivity or acute respiratory distress syndrome. The patient should receive appropriate treatment. Permanently discontinue ocrelizumab in these patients.

IRR = infusion-related reaction.

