5.3.3 Assessment of Severity of Adverse Events

The adverse event severity grading scale for the NCI CTCAE (v4.0) will be used for assessing adverse event severity. [Table 3](#) will be used for assessing severity for adverse events that are not specifically listed in the NCI CTCAE.

Table 3 Adverse Event Severity Grading Scale for Events Not Specifically Listed in NCI CTCAE

Grade	Severity
1	Mild; asymptomatic or mild symptoms; clinical or diagnostic observations only; or intervention not indicated
2	Moderate; minimal, local, or non-invasive intervention indicated; or limiting age-appropriate instrumental activities of daily living ^a
3	Severe or medically significant, but not immediately life-threatening; hospitalization or prolongation of hospitalization indicated; disabling; or limiting self-care activities of daily living ^{b,c}
4	Life-threatening consequences or urgent intervention indicated ^d
5	Death related to adverse event ^d

NCI CTCAE = National Cancer Institute Common Terminology Criteria for Adverse Events.

Note: Based on the most recent version of NCI CTCAE (v4.0), which can be found at: http://ctep.cancer.gov/protocolDevelopment/electronic_applications/ctc.htm

- ^a Instrumental activities of daily living refer to preparing meals, shopping for groceries or clothes, using the telephone, managing money, etc.
- ^b Examples of self-care activities of daily living include bathing, dressing and undressing, feeding oneself, using the toilet, and taking medications, as performed by patients who are not bedridden.
- ^c If an event is assessed as a "significant medical event," it must be reported as a serious adverse event (see Section 5.4.2 for reporting instructions), per the definition of serious adverse event in Section 5.2.2.
- ^d Grade 4 and 5 events must be reported as serious adverse events (see Section 5.4.2 for reporting instructions), per the definition of serious adverse event in Section 5.2.2.

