5.3.5.1 Infusion-Related Reactions

Adverse events that occur during or within 24 hours after study drug administration and are judged to be related to study drug infusion should be captured as a diagnosis (e.g., “infusion-related reaction” or “anaphylactic reaction”) on the Adverse Event eCRF. If possible, avoid ambiguous terms such as “systemic reaction.” Associated signs and symptoms should be recorded on the dedicated Infusion-Related Reaction eCRF. If a patient experiences both a local and systemic reaction to the same dose of study drug, each reaction should be recorded separately on the Adverse Event eCRF, with signs and symptoms also recorded separately on the dedicated Infusion-Related Reaction eCRF.

Investigators should consider a local IRR for any symptoms affecting the skin and localized to only one place. Any other IRR should be considered systemic.

Further details on prevention and management of IRRs are described in Section 5.1.3.1.1, Section 5.1.4 (Table 2), and in the Ocrelizumab Investigator’s Brochure.

Ocrelizumab—Genentech, Inc.
50/ Protocol MN30035, Version 5

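### The shorter-infusion substudy's rule for a Grade 3 infusion-related reaction can be met by slowing alone, which is looser than the interruption that Section 5.1.4 Table 2 directs, and Appendix 2 does not cite that table

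*Protocol*

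**What the plan says.** The substudy gives 600 mg over about 2 hours instead of 3.5 hours. Protocol Appendix 2, under Study Design, states: "Ocrelizumab infusion rate will be slowed and/or stopped if a patient experiences a Grade 3 or higher IRR or other serious adverse event". SAP Appendix 6, under Substudy Design, has the same sentence.

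Section 5.1.4 Table 2 of the main protocol has three tiers. For mild to moderate IRRs the rate is halved for at least 30 minutes. For severe IRRs: "If a patient experiences a severe IRR or a complex of flushing, fever, and throat pain symptoms, the infusion should be interrupted immediately". It continues: "The infusion should be restarted only after all symptoms have resolved", and "The initial infusion rate at restart should be half of the infusion rate at the time of onset of the reaction". For life-threatening or disabling IRRs the drug is stopped and permanently discontinued.

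Appendix 2 refers to main-study Section 4.3.3 for premedication and Section 5.2.2 for seriousness. For managing specific adverse events it points to the Investigator's Brochure. It does not cite Section 5.1.4. The only Table 2 that it names is its own sample-size table.

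**The concern.** The sentence in Appendix 2 is the only place where the substudy text says what to do with the infusion rate for a Grade 3 IRR. Because it offers slowing or stopping, a site that only turns the rate down has followed it. Under Section 5.1.4, slowing without interruption is the response to mild to moderate reactions only.

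So, in an infusion faster than the approved one, the substudy wording is more permissive than the main protocol for the very event that the substudy is set up to measure. Followed as worded, it could keep drug running through a Grade 3 reaction. Eligibility does not remove such patients: Appendix 2 excludes those with a prior serious IRR, and Section 5.2.2 says that severe and serious are different things, so a patient with an earlier non-serious Grade 3 IRR may enrol.

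**Working it through.** This is mainly a comparison of texts.

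**1. Does severe mean Grade 3?** Section 5.3.3 Table 3 describes Grade 3 as "Severe or medically significant, but not immediately life-threatening". That table is written for events not listed in CTCAE, so it is the nearest mapping rather than an exact one. Section 4.6.2 supports it by equating a life-threatening infusion-related event with Grade 4. That leaves Grade 3 for Table 2's middle tier.

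**2. The two rules by grade.**

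| IRR | Section 5.1.4 Table 2 | Appendix 2 | Consistent? |
|---|---|---|---|
| Grade 3 (severe) | Interrupt at once; restart at half rate after full resolution | Slow, stop, or both | Appendix 2 is looser |
| Grade 4 (life-threatening) | Stop; discontinue permanently | Discontinuation required under Dosage Modification | Yes |

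A site that interrupts and then restarts at half rate satisfies both texts. A site that only slows satisfies Appendix 2 but not Table 2.

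**3. What slowing leaves running.** Appendix 2 Table 1 reproduces: 120 × 0.25 + 240 × 0.25 + 300 × 0.5 + 360 × 0.5 + 360 × 0.5 = 30 + 60 + 150 + 180 + 180 = 600 mg in 120 minutes. Appendix 2 gives no size for the reduction. After slowing, the rate is therefore somewhere between 0 and the scheduled rate at onset: below 120 mg/h in the first 15 minutes and below 360 mg/h in the last hour. Under interruption it is 0 until symptoms resolve. Nothing narrower follows from the documents.

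**4. How many patients.** Appendix 2's background says that more than 90% of patients with IRRs had mild to moderate ones, so fewer than 10% had worse. That is earlier experience at slower infusion. If the share carried over, the expected number among 100 substudy patients would be below 100 × 0.10 = 10 even if every patient reacted. It would be below 100 × 0.343 × 0.10 = 3.4 at the 34.3% IRR proportion that Section 1.2.1.2 gives for the pooled relapsing-MS trials. Both are scale only, since the documents give no IRR rate for the two-hour infusion.

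**5. Effect on the analysis.** The outcome is the proportion of patients with a Grade 3 or 4 IRR. A patient is in that count once the reaction reaches Grade 3, whatever is then done to the rate. The exact (Clopper-Pearson) limits depend only on the count and n = 100, and the plan's limits reproduce (1/100: 0.03% to 5.45%; 7/100: 2.86% to 13.89%). Only the descriptive summaries of interventions and infusion duration could differ according to which text a site follows.

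**The case against.** The strongest reply is that Appendix 2 should not be read alone. It belongs to the same protocol, and nothing in it sets Section 5.1.4 aside. Section 5.3.5.1 sends IRR management to Table 2 without restriction. Appendix 2's safety plan relies on "protocol-specified ocrelizumab treatment interruption criteria", the phrase that Section 5.1 uses in opening the Safety Plan that contains Table 2. Its background mentions guidance on adjusting the infusion. One sentence also has to cover Grade 3, Grade 4 and other serious events, so its wording must be broad. Table 2 itself is headed as guidelines and says what should be done. The Investigator's Brochure, not available here, may repeat the same actions. Finally, infusions are closely supervised, and the SAP lists the action taken for each Grade 3 or 4 IRR, so differences in practice would be visible.

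Most of this stands. It shows that Table 2 was probably intended, and it keeps the severity low. It does not change the sentence: a generic phrase without a section number does not tell a site that slowing alone is insufficient at Grade 3, and recording the action afterwards does not guide it at the bedside.

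Two stronger readings are tempting. A reader might infer that the substudy waives interruption or contradicts the main protocol. The documents do not support that, since both texts can be followed at once. A reader might also infer that mild to moderate IRRs have no rule in the substudy. Appendix 2 merely omits that detail; Table 2 supplies it and is not disapplied.

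**Conclusion.** The point holds as a difference in permissiveness together with a missing cross-reference, confined to Grade 3 IRRs in the substudy. It rests on reading severe as Grade 3, which Sections 4.6.2 and 5.3.3 support without stating it for IRRs specifically. Table 2 directs interruption as a guideline; calling it a strict requirement would overstate it.

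No dose excess or patient count is claimed. Assuming particular percentage cuts for the slowing would produce figures that only restate the assumption. The primary substudy outcome, the sample size of 100 and the confidence intervals are unaffected. The correction is worth making because the looser rule sits in the text written for the faster infusion, and because the protocol gives no reason for a looser rule if one was intended. Severity is low.

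**What to change.** In Protocol Appendix 2 (Study Design) and SAP Appendix 6 (Substudy Design), replace the sentence with:

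*IRRs during the shorter infusion are managed per Section 5.1.4 Table 2 of the main protocol; for a Grade 3 (severe) IRR the infusion is interrupted immediately and is restarted, at half the rate at onset, only once all symptoms are gone. For any other serious adverse event, the infusion is slowed and/or stopped.*

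Give the section number, because Appendix 2 has a Table 2 of its own. If the substudy is meant to depart from the main-study guideline, say where and why instead. The SAP listings and intervention categories need no change. The cost is one sentence becoming two in each document, with no extra data, patients or analyses.

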Appendix 2 ***Optional Shorter Infusion Substudy (cont.)***

SAFETY PLAN

Identified and potential risks associated with ocrelizumab treatment will continue to be closely monitored throughout the substudy. Patient safety will be ensured by targeting the most appropriate patient population, stringent safety monitoring by the Sponsor, and protocol-specified ocrelizumab treatment interruption criteria. Patients will be evaluated clinically before and during their participation in this substudy. Safety evaluations will consist of medical interviews, recording of adverse events, and physical examinations. Adverse events will be graded according to NCI CTCAE v4.0.

Administration of ocrelizumab will be performed in a hospital or clinic environment under close supervision of the investigator or a medically qualified staff member. All adverse events and serious adverse events will be recorded during the substudy for at least 30 days after treatment (i.e., the substudy follow-up period). Safety assessments will include the incidence, nature, and severity of (serious) adverse events graded per the NCI CTCAE v4.0. Safety assessments will be conducted per the substudy schedule of activities.

The identified and potential safety issues anticipated in this substudy, including IRRs, are reported in the Ocrelizumab Investigator's Brochure. Guidelines for the management of patients who experience specific adverse events are also included in the Ocrelizumab Investigator's Brochure.

PATIENT SELECTION CRITERIA

Inclusion Criteria

Patients must continue to meet the following:

- *Actively enrolled in the main study*
- *Completed Week 72 infusion*
- *Signed substudy Informed Consent Form prior to the Week 96 infusion*
- *Able to comply with the substudy protocol, in the investigator's judgment*

Exclusion Criteria

Patients who become ineligible for any reason in the main study, in addition to the following:

- *Any documented serious IRR at any time during the main study*

TRIAL DRUG

Dosage, Administration, and Storage

Patients will receive 600-mg IV ocrelizumab per a shorter infusion protocol (see Table 1).

Ocrelizumab—Genentech, Inc.
81/ Protocol MN30035, Version 5

Appendix 2
Optional Shorter Infusion Substudy (cont.)

Table 1: Infusion Rates for 600-mg Ocrelizumab Shorter Dose

Time (min)	Infusion rate (mL/hr)	Infusion rate (mg/hr)	Max Dose per Interval (mg)	Cumulative Dose (mg)
0–15	100	120	30	30
15–30	200	240	60	90
30–60	250	300	150	240
60–90	300	360	180	420
90–120	300	360	180	600

Infusion time: 120 min.

Preparation per U.S. label: 600 mg ocrelizumab/500 mL normal saline toward a drug concentration of approximately 1.2 mg/mL.

Although ocrelizumab may be administered on an outpatient basis, patients may be hospitalized for observation at the discretion of the investigator. Ocrelizumab infusions should always be administered in a hospital or clinic environment under close supervision of the investigator or a medically qualified staff member.

To reduce potential IRRs, all patients will receive prophylactic treatment with 100 mg of methylprednisolone (or equivalent steroid), to be completed approximately 30 minutes before the start of each ocrelizumab infusion, and with an antihistaminic drug (e.g., diphenhydramine) approximately 30–60 minutes before each ocrelizumab infusion.

It is also strongly recommended that the infusion is accompanied by prophylactic treatment with an analgesic/antipyretic such as acetaminophen/paracetamol (1 g) 30–60 minutes prior to the start of an infusion to reduce potential IRRs.

Since transient hypotension may occur during ocrelizumab infusion, the investigator may wish to withhold anti-hypertensive medications 12 hours prior to ocrelizumab infusion.

Ocrelizumab must not be administered as an IV push or bolus. Well-adjusted infusion pumps should be used to control the infusion rate, and ocrelizumab should be infused through a dedicated line. It is important not to use evacuated glass containers, which

Ocrelizumab—Genentech, Inc.
 82/ Protocol MN30035, Version 5

Appendix 2 **Optional Shorter Infusion Substudy (cont.)**

require vented administration sets, to prepare the infusion because this causes foaming as air bubbles pass through the solution.

After completion of the infusion, the IV cannula should remain in situ for at least 1 hour to allow for administration of drugs intravenously, if necessary, in the event of a delayed reaction. If no adverse events occur during this period of time, the IV cannula may be removed and the patient may be discharged.

See the Ocrelizumab IB for detailed instructions on drug preparation, storage, and approved administration.

Dosage Modification

Unless an IRR occurs necessitating discontinuation, the entire contents of the infusion bag must be administered to the patient.

Patients must discontinue study treatment if they experience any of the following:

- *Life-threatening IRR or serious hypersensitivity reaction*
- *Active hepatitis B infection*
- *Progressive multifocal leukoencephalopathy (PML)*
- *Active tuberculosis, either new onset or reactivation*

SUBSTUDY ASSESSMENTS

Substudy assessments will be performed according to the schedule of activities in Table 3.

Informed Consent Forms and Screening Log

Written informed consent for participation in the substudy must be obtained before performing any substudy-related procedures.

Physical Examinations

A limited physical examination will be conducted at the substudy treatment visit. Any abnormality identified prior to treatment administration in the substudy should be recorded on the eCRF. New or worsened clinically significant abnormalities after treatment administration should be recorded as adverse events, if appropriate.

Vital Signs

Vital signs will include measurements of heart rate, temperature, and systolic and diastolic blood pressure.

Ocrelizumab—Genentech, Inc.
83/ Protocol MN30035, Version 5

Appendix 2 **Optional Shorter Infusion Substudy (cont.)**

Vital signs should be taken approximately 45 minutes prior to premedication. In addition, vital signs should be obtained prior to the ocrelizumab infusion and then approximately every 15 minutes for the first hour, followed by approximately every 30 minutes until 1 hour after the end of the infusion.

Patients will be informed about the possibility of delayed post-infusion symptoms and instructed to contact their study physician if they develop such symptoms.

SUBSTUDY FOLLOW-UP

Patients should have substudy follow-up 30 days after the date of the last infusion of ocrelizumab in this substudy, consisting of one clinic visit. After 30 days, patients may continue to be followed per the main study safety follow-up if they do not continue onto commercial ocrelizumab.

STATISTICAL METHODS

Safety Analyses

Safety analyses will include all patients who received any amount of study treatment in the substudy.

Safety will be summarized using descriptive statistics. Continuous variables will be summarized using n (sample size), mean, standard deviation, median, minimum, and maximum. Frequency distributions (patient counts and associated percentages) will be used to summarize categorical variables. When applicable, 95% confidence intervals (CIs) will be provided for the mean and proportion. The Clopper and Pearson method will be used to calculate exact CIs for proportion when applicable.

All adverse events occurring on or after treatment will be coded, summarized by NCI CTCAE v4.0 grade, and tabulated by body system and Preferred Term for individual adverse events within each body system. Grade 3 to 5 adverse events, serious adverse events, adverse events leading to treatment discontinuation, time to withdrawal from the study due to an adverse event, adverse events leading to infusion adjustment, and treatment-related adverse events will be summarized. In addition, all serious adverse events and deaths will be listed.

Associated laboratory parameters, such as hepatic function, renal function, and hematology values, will be grouped and presented together. Marked abnormalities will also be flagged.

Ocrelizumab exposure will be summarized, including rate of infusion and dosage.

Ocrelizumab—Genentech, Inc.
84/ Protocol MN30035, Version 5

